4.2.3 Administration of study drugs

All study drugs will be administered in the clinical research facility or oncology treatment suite of the respective study centres where trained personnel, resuscitation equipment and emergency drugs are immediately available. Vital signs will be measured before and after administration of all investigational products. The doctor/nurse will wear gloves and eye protection. Patients will remain in the unit for 1 hour (+/- 15 min) for observation after each vaccination and 30 min (+/- 15 min) for observation after each checkpoint inhibitor treatment.

ChAdOx1.5T4 and MVA.5T4 vaccines

The vaccines will be allowed to thaw to room temperature and will be administered by intramuscular injection within 1 hour of removal from the freezer. The preferred site for vaccination is the vastus lateralis muscle of the thigh but the deltoid muscle of the arm is an acceptable alternative. It is advised to use a different thigh (arm) for each of the two MVA.5T4 immunisations.

Immune checkpoint inhibitor nivolumab (Opdivo®)

Nivolumab 480mg, will be prepared from 10mg/ml concentrate, diluted into sodium chloride 9 mg/mL (0.9%) solution for injection and administered intravenously in a volume of 100ml to a final concentration of 4.8mg/ml. Preparation and handling will adopt strict aseptic technique. In line with the manufacturer's instructions, nivolumab will be administered intravenously over a period of 60 minutes using a volumetric pump, an infusion set and an in-line, sterile, non-pyrogenic, low protein binding filter of pore size of 0.2µm to 1.2µm. After administration the line will be flushed with sodium chloride 9 mg/mL (0.9%) solution for injection.

4.3. Allocation to study groups and dosing regime

The 36 subjects will be recruited to the study: 12 patients with low- or intermediate-risk prostate cancer (Group 1) and 24 patients with metastatic prostate cancer (Group 2).

Group 1: Low- or intermediate-risk localised or locally advanced prostate cancer patients scheduled to undergo radical prostatectomy

12 subjects will be treated with ChAd-MVA.5T4 vaccination plus 1 dose of the anti-PD-1 monoclonal antibody Nivolumab

Week 0:	ChAdOx1.5T4	2.5×10^{10} vp	intramuscular injection
Week 1:	MVA.5T4	2×10^8 pfu	intramuscular injection
	Nivolumab	480mg	intravenous infusion

Group 2: Metastatic prostate cancer patients with disease progression on anti-androgen therapy with either enzalutamide or abiraterone

24 subjects will be treated with ChAd-MVA.5T4 vaccination plus 3 doses of the anti-PD-1 monoclonal antibody Nivolumab

Week 0:	ChAdOx1.5T4	2.5×10^{10} vp	intramuscular injection
Week 4:	MVA.5T4	2×10^8 pfu	intramuscular injection
	Nivolumab	480mg	intravenous infusion
Week 8:	Nivolumab	480mg	intravenous infusion
Week 12:	ChAdOx1.5T4	2.5×10^{10} vp	intramuscular injection
	Nivolumab	480mg	intravenous infusion
Week 16:	MVA.5T4	2×10^8 pfu	intramuscular injection

Compliance with Dosing Regimen

Administration of all vaccines and checkpoint inhibitor therapies will be undertaken by a delegated research nurse or investigator in the clinical research facility or oncology treatment suite of the respective study centres. All study treatments will be recorded in the CRF and the relevant accountability log by the research nurse or investigator. There are no self-administered investigational products involved in this study.

4.4. Duration of study

Subjects undergoing radical prostatectomy will all be followed up for a total duration of 6 months from enrolment. Planned follow up for participants with metastatic prostate cancer is 12 months from enrolment.

4.5. Definition of the Start and End of the Study

The start of the study is defined as the date of the first administration of a study drug. The end of the study is three months after the last visit of the last subject to allow for sample analysis.

4.6. Potential risks to participants

Risks to participants in this Phase II study can be divided as follows:

4.6.1 Phlebotomy

The volume of blood drawn over the study period (up to 616ml) should not compromise patients, as during any one normal blood donation a total volume of 470ml can be drawn and the procedure is allowed for up to 3 times a year according to the NHS regulations.

Local reactions to vaccine, venepuncture or intravenous cannulation

Mild tenderness, bruising, light-headedness or, rarely, syncope, may result from venepuncture. Vaccine-related side effects are believed to be related more to the vectors used rather than the specific insert.

4.6.2 Surgery delay

Surgery is expected to take place at least 4 weeks post nivolumab infusion. The risk associated with postponing surgery for low and intermediate risk prostate cancer by a maximum of approximately 6 weeks is difficult to accurately quantify but the researchers consider it to be very small for men with this type of prostate cancer. Indeed, many men with low- and intermediate-risk prostate cancer do not need any immediate treatment at all, and some choose “active surveillance” and potentially delay treatment for many years (or can avoid treatment altogether) in order to avoid treatment-related side effects and potential “over-treatment” of clinically insignificant forms of prostate cancer, rather than undergo immediate treatment with surgery or radiotherapy. Patients with high-risk prostate cancer, where the effect of a 6-week delay might be significant, will not be included in this study. Seventeen studies have investigated the effect of delaying surgery for low and intermediate risk prostate cancer⁴². None of these studies reported lower chance of cure for patients with low risk cancer if surgery delayed for up to several years. Many patients with low risk prostate cancer do not need any treatment at all, but may still opt for surgery rather than active surveillance. One of these studies reported higher risk of recurrence if surgery for intermediate risk cancer was delayed for more than 9 months, but in the other 16 studies no significant negative effect was found among men who had delayed surgery⁴². Patients with high-risk prostate cancer, on the other hand, should be treated without delay and are therefore not eligible for the ADVANCE study. In summary, the researchers therefore believe that a 6-week delay of surgery for men in this study, all of whom have been diagnosed with low or intermediate risk prostate cancer, in order for them to receive their vaccinations poses very little risk with regards a change in the potential of the surgery to cure them of their prostate cancer. All patients will have a mpMRI scan before enrolment that will minimize the risk of any patient with a high-risk cancer being misclassified as low or intermediate risk.

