5.2. Informed consent

All patients will sign and date the informed consent form before any study-specific procedures are performed. The information sheet will be made available to the patient at least 24 hours prior to the screening visit. The patient will be fully informed of all aspects of the trial, the potential risks and their obligations. The following general principles will be emphasised:

- Participation in the study is entirely voluntary
- Refusal to participate involves no penalty or loss of medical benefits
- The patient may withdraw from the study at any time
- The patient is free to ask questions at any time to allow him or her to understand the purpose of the study and the procedures involved
- The study involves research of an investigational vaccine and checkpoint inhibitor
- The study involves delaying the patient's surgery by approximately 2 months
- There may be no direct benefit for participating

The aims of the study and all tests to be carried out will be explained. The patient will be given the opportunity to ask about details of the study, and will then have time to consider whether or not to participate. If they do decide to participate, they will sign and date the consent form, which will also be signed and dated by the investigator. One copy will be given to the participant, one copy will be placed in the study file, and the original will be placed in their medical notes.

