- **Exploratory Biochemistry:** Four kallikrein peptidases blood test
- **Circulating tumour DNA (ctDNA) and circulating tumour cell (CTC) quantification assays**

Other tests, e.g. immunological assays including ELISPOT assays for other cytokines, T cell epitope mapping, RNA and DNA sequencing or other methods of analysis of genetic polymorphism

potentially relevant to the investigational products may also be performed at the discretion of the investigators.

Multi-parametric Magnetic resonance imaging (mpMRI) – Group 1

Participants in group 1 who are planned to undergo radical prostatectomy will undergo an mpMRI of the prostate and pelvis prior to enrolment on the study as part of standard care in the prostate cancer diagnostic pathway. The subjects who had a pelvic / prostate mpMRI of adequate quality before screening and enrolment will have a repeat on-study mpMRI to evaluate any post-treatment radiographic change in the prostate. The on-study mpMRI should take place prior to radical prostatectomy and a minimum of 7 days after final study checkpoint inhibitor therapy, i.e. on or after study week 4 +7 days. Participants, whose pre-enrolment pelvis/prostate mpMRI is, in the opinion of the reporting radiologist, of low diagnostic value (for example, images are significantly degraded by artefact or post-biopsy haemorrhage), are not required to undergo a repeat on-study mpMRI as the baseline scan will not provide adequate comparator for post-treatment changes. Conventional three-planar MRI including T1 and T2 weighted DCE-MRI and diffusion-weighted sequences will be performed on a 1.5 T magnet. Areas of signal abnormality suspicious for malignancy within the prostate will be graded according to PIRADS criteria. Local T-stage disease identified on scans will be reported as per European consensus on prostate MRI⁴³. The procedure will be performed at the Oxford University Hospitals NHS Foundation Trust and the Christie Hospital NHS Foundation Trust clinical sites.

Tumour Assement by CT scan, bone scintigraphy, MR scan – Group 2

Radiological tumour assessments will be performed at baseline (28 day sceening period), at 6 months and 12 months. The assessments will include a CT scan of chest, abdomen and pelvis and bone imaging, e.g. bone scans or body MRI. CT and MR imaging will be performed with contrast unless this is contraindicated for medical reasons.

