12.3. Informed Consent

Written informed consent will be obtained at screening as detailed in section 5.2.

12.4 . Surgery delay

The risk associated with postponing surgery by approximately 6 weeks is considered very small as detailed in section 4.6.2. The investigators will discuss this issue with the potential participants in detail. The patients who require an operation without delay are not eligible for this study.

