APPENDIX 1: SCHEDULE OF ATTENDANCE AND STUDY PROCEDURES

Group 1: Participants scheduled for Radical Prostatectomy

Visit/Telephone Call Number	S	V1	T1	V2	T2	V3	V4		V5	V6
Time from enrolment (weeks +days)	≤ -4	0	0+2	1	1+2	2	5	≥5	16	24
Window (days) *	0		=3	+3	+3	+3	±7	+14	±7	±7
Informed consent	X									
Review of inclusion criteria	X	X								
Review of exclusion criteria	X	X		X		X	X		X	X
Medical history	X	(X)		(X)		(X)	(X)		(X)	(X)
Physical examination	X									
Targeted physical examination		(X)		(X)		(X)	(X)		(X)	(X)
Retrieval of archival diagnostic biopsy		X**								
Fresh biopsy (if required)		X**								
Telephone call			X		X					
Recording vital signs	X	X		X		X	X		X	X
ECOG Status	X								X	X
ChAdOx1.5T4 vaccination		X								
MVA.5T4 vaccination				X						
Nivolumab infusion				X						
Radical Prostatectomy (mpMRI – optional)								X		
Assessment & recording of adverse events		X	X	X	X	X	X		X	X
Patient alert card provided				X						
Diary card provided		A		C						
Diary card returned				X			X			
Haematology ¹	2	2		2		2	2		2	2
Biochemistry ¹	4	4		4		4	4		4	4
Serum glucose ¹	2	2		2		2	2		2	2
Thyroid function tests ^{1,2}	2	2					2			2
PSA ¹	5	5		5		5	5		5	5
Urinalysis	X	X		X		X	X		X	X
HBVsAg, HIV &HCV Ab ¹	5									
Human leukocyte antigen typing (ml)		5								
Exploratory immunology (ml)		50		50		50	50		50	50
Exploratory biochemistry (ml)		2		2		2	2		2	2

Total blood volume per visit (ml) ¹	20	70		65		65	67		67
Cumulative blood volume ≈ 421ml¹									

* Window is based on preceding IMP administration

** Window is -28 days

¹Volume can vary by site according to local practices

² Total triiodothyronine (T3) or free T3c, free thyroxine (T4) and thyroid stimulating hormone (TSH)

Group 2: Participants with Metastatic Prostate Cancer

Table of events (part 1 of 2)

Visit/Telephone Call Number	S	V1	T1	V2	V3	T2	V4	V5	T3	V6
Time from enrolment (weeks+days)	≤-4	0	0+2	2	4	4+2	5	8	8+2	9
Window (days)*			+3	±2	±2	+3	+3	±2	+3	+3
Informed consent	X									
Review of inclusion/exclusion criteria	X	X		(X)	X		(X)	X		(X)
Medical history	X	(X)		(X)	(X)		(X)	(X)		(X)
Physical examination (if required)	X	(X)		(X)	(X)		(X)	(X)		(X)
Retrieval of archival diagnostic biopsy		X ¹								
Fresh biopsy (if required)		X ¹								
Telephone Call			X			X			X	
Recording vital signs	X	X		X	X		X	X		X
ECOG Status	X				X			X		
ChAdOx1.5T4 vaccination		X								
MVA.5T4 vaccination					X					
Nivolumab infusion					X			X		

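### The protocol gives inconsistent figures for the Group 1 surgery delay in its risk assessment, consent principles and schedule, and its mpMRI safeguard is not tied to the entry rules

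*Protocol*

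**What the plan says.** **Delay of surgery.** The risk argument in section 4.6.2 concerns postponement "by a maximum of approximately 6 weeks" and expects surgery no sooner than 4 weeks after nivolumab. Section 12.4 refers back to it: "The risk associated with postponing surgery by approximately 6 weeks is considered very small as detailed in section 4.6.2". Section 5.2, in its list of principles for the consent discussion, has: "The study involves delaying the patient's surgery by approximately 2 months". In Appendix 1 (Group 1), nivolumab falls at week 1 with a +3 day window. Prostatectomy has its own column at 5 weeks or later with a +14 day window. Section 5.5 allows a dose to be held, for example for fever or intercurrent illness, and sets no time limit. No section states the date from which the delay is counted.

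**mpMRI.** Section 4.6.2 says that high-risk men should not wait for surgery and closes with: "All patients will have a mpMRI scan before enrolment that will minimize the risk of any patient with a high-risk cancer being misclassified". Section 6.2 plans the scan: Group 1 participants "will undergo an mpMRI of the prostate and pelvis prior to enrolment on the study as part of standard care". The same paragraph covers participants whose pre-enrolment scan the radiologist considers of low diagnostic value. They "are not required to undergo a repeat on-study mpMRI as the baseline scan will not provide adequate comparator for post-treatment changes". The Group 1 criteria in section 5.3 cover histology, Gleason score, local stage, nodal and metastatic status, PSA, operability and the absence of a need for urgent surgery. They mention neither the scan nor its quality.

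**The concern.** The delay is the main burden that the study design places on men who could otherwise go straight to curative surgery. The risk assessment and the consent discussion ought to describe the same delay, and the schedule ought to stay within it. Here the conclusion of very small risk is argued for one figure, men are to be told another, and the visit schedule permits a third range. Because 12.4 also has investigators discuss the postponement in detail with reference to 4.6.2, the same man could hear both 6 weeks and 2 months.

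The mpMRI point bears on the same justification. The delay studies cited in 4.6.2 concern low- and intermediate-risk disease, so they offer no reassurance about a man wrongly placed in that category. Section 4.6.2 gives mpMRI the task of limiting that error. If a man can enter with a scan of low diagnostic value, that task is done less well for him than the text claims.

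**Working it through.** No sample-size formula applies. The check is calendar arithmetic on the protocol's own schedule, followed by a comparison of sections.

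**Inputs.** Nivolumab on Day 7 (4.3, 6.1); at least 4 weeks (28 days) from nivolumab to surgery (4.6.2); surgery at 5 weeks or later, window +14 days (Appendix 1); week 1 visit window +3 days (Appendix 1); stated delays of about 6 weeks (4.6.2, 12.4) and about 2 months (5.2).

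**Schedule, counted from the first vaccination.**
- Earliest surgery: 7 + 28 = 35 days = 5.0 weeks. This reproduces the 5-week entry in Appendix 1.
- With the surgery window: 35 + 14 = 49 days = 7.0 weeks.
- With the week 1 window as well: 7 + 3 + 28 + 14 = 52 days = 7.4 weeks.
- With the Day 7 dose held under 5.5: later still, by an amount that the protocol does not bound.

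**Stated figures.**
- 6 weeks = 42 days. This lies inside the 35 to 52 day range but is not its upper end. The schedule exceeds it by 49 − 42 = 7 days, or 52 − 42 = 10 days.
- 2 months = 2 × 365.25 / 12 = 60.9 days = 8.7 weeks. This exceeds 6 weeks by 60.9 − 42 = 18.9 days, and 60.9 / 42 = 1.45, so it is 45% longer. Read as 8 weeks, the difference is 56 − 42 = 14 days.

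| Place | Delay | Days |
|---|---|---|
| 4.6.2 | at most about 6 weeks | 42 |
| 12.4 | about 6 weeks | 42 |
| 5.2 | about 2 months | 60.9 |
| Appendix 1 | 5.0 to 7.4 weeks | 35 to 52 |

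**mpMRI, sections compared.**
- 4.6.2: every patient is scanned before enrolment, to limit misclassification.
- 6.2: the scan is planned as standard care; a man whose scan is of low diagnostic value is still called a participant and is only excused the repeat scan.
- 5.3: no criterion refers to the scan or its adequacy.

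Taken together, 6.2 and 5.3 allow a man with a poor scan to enter. No sentence says so outright; it is an inference from the two sections.

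**The case against.** The strongest reply is that little harm follows. By the account in 4.6.2, none of the 17 cited studies found a lower chance of cure in low-risk men with delays of up to several years. One found more recurrence in intermediate-risk men, after more than 9 months (9 × 365.25 / 12 = 273.9 days, or 39.1 weeks). Delays of 7.4 or 8.7 weeks are far inside that. Both stated figures are approximate, the schedule is centred near 6 weeks, and the consent figure errs on the long side: 60.9 days exceeds the 52 that the visit windows allow. This stands as a limit on the likely harm. It does not remove the contradiction, since 19 days on a base of 42 is more than rounding and 4.6.2 calls its figure a maximum.

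On mpMRI, it is fair to say that the scan is a supporting argument and that 5.3 screens independently: Gleason score no higher than 7, no Gleason 5 disease, PSA no higher than 20 ng/ml, a stage limit, and operability judged by the consultant surgeon. A poor scan removes none of these limits. That stands, and makes this the secondary point.

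Several stronger readings are tempting but not supported:
- *No pre-enrolment scan is required.* Sections 4.6.2 and 6.2 both plan one. The gap concerns adequacy as a condition of entry.
- *Appendix 1 makes the safeguard scan optional.* The optional mpMRI sits in the surgery column at 5 weeks or later, so it is the post-treatment scan.
- *The true delay reaches 11 weeks.* That adds a 4-week screening allowance to 7 weeks, and nothing in the protocol says that screening itself postpones surgery.
- *A given number of high-risk men will enter, or the PSA result will be distorted.* The protocol gives no rate of poor scans or of misclassification among such men, and Group 1 is sized for an initial descriptive comparison.

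**Conclusion.** The delay figures contradict one another in current text, independently of the amendment log. The risk assessment covers about 42 days, the consent principle about 61, and the schedule 35 to 52 or more. The stated maximum is exceeded by 7 to 10 days within the permitted visit windows, and consent differs from the risk assessment by about 19 days (14 if 2 months means 8 weeks). These sizes assume counting from the first vaccination, because the protocol fixes no starting point. The information sheet is not among the documents, so what men are actually told is known only from the principle in 5.2.

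Secondarily, the mpMRI safeguard as worded in 4.6.2 is weakened for men whose scan is of low diagnostic value. The number of such men cannot be stated from the protocol. The other risk criteria in 5.3 continue to apply to them.

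This should be corrected. It bears on consent and on the stated basis for accepting the delay, but it does not show that the delay is unsafe.

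**What to change.** Reconcile sections 4.6.2, 5.2, 12.4 and Appendix 1 to one delay figure, counted from one stated starting point. Make clear how that figure relates to the surgery window and to a held Day 7 dose. Check the information sheet against it. Separately, reconcile the mpMRI statement in 4.6.2 with sections 5.3 and 6.2, so that the safeguard claimed is the one that the entry rules deliver. Which delay figure and which scan rule apply is for the clinicians to decide.

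The cost is mainly wording in these sections, plus a check and possible revision of the information sheet. If the reconciliation changes an entry rule or the schedule, it would go through the protocol's own route for substantial amendments.

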4.6.3 Risks associated with study vaccinations

Vaccination may precipitate a local inflammatory reaction. This may include swelling, tenderness or erythema. Systemic reactions that could potentially occur following immunisation with a recombinant ChAdOx1 and MVA vaccines include constitutional manifestations resembling flu such as fever, headache, rash, malaise, fatigue, anorexia, arthralgia, and myalgia. These are typically self-limiting over a period of 48-72 hours following ChAd-MVA.5T4 monotherapy. Allergic and hypersensitivity reactions to the vaccine are a reasonable expectation. Severe hypersensitivity reactions to the vaccine are rare and should be managed in accordance with Advanced Life Support algorithms. Immunological sequelae following any immunisation are recognised but rare. These are however associated with checkpoint inhibitor therapy as discussed below.

4.6.4 Risks associated with checkpoint inhibitor therapy

Extravascular infiltration

In the event of inadvertent infiltration into the extravascular compartment subjects may experience localised irritation and discomfort, including swelling and erythema. However, nivolumab (Opdivo®) is a non-vesicant drug and therefore does not confer risk of extravasation tissue necrosis. No specific neutralising or dispersal interventions are indicated. The potential for extravascular infiltration will be minimised by careful selection of the cannulation site and close monitoring of the subject during the infusion. At the earliest appearance of extravascular infiltration the infusion will be stopped, the device removed and the site cared for according to local guidance.

Infusion reaction

At the time of licencing the overall incidence of hypersensitivity/infusion reactions associated with nivolumab monotherapy was 5.0%. The majority of infusion reactions are mild in severity and are evident within 2 hours of the infusion. Hypersensitivity reactions may manifest as:

- Flushing or itching or rash
- Nausea or vomiting
- Fever or chills
- Dyspnoea, wheeze or chest discomfort
- Hypotension and changes to vital signs

All infusion reactions will be graded and recorded as adverse events according to NCI CTCAE v4.0 criteria and managed in line with established site-specific treatment algorithms. All treatments will be undertaken by oncology nurses experienced in the management of intravenous therapies and take place in a treatment facility with access to resuscitation equipment and a medical emergency / resuscitation team. Severe infusion reactions and anaphylaxis will be managed according to Advanced Life Support protocols.

General side effects

The most frequent side effects of immune checkpoint inhibitor therapy are fatigue, decreased appetite and nausea which each affect between 20 and 50% of cancer patients receiving continuous checkpoint inhibitor treatment in recent Phase III clinical trials. There is limited data on the side effects of short term immune checkpoint inhibitors.

Immune mediated toxicity

Checkpoint inhibitor treatment is associated with immune-mediated adverse reactions which may affect any organ system. Current data on the incidence of immune-related toxicities are derived from a number of large phase III clinical trials administering weeks to months of continuous checkpoint inhibitor therapy until disease progression, loss of clinical benefit or unacceptable toxicity, in a range of non-prostate tumour types. This study, however, will make use of a **restricted course of treatment limited to 3 infusions 4 weeks apart for metastatic PCa patients and only 1 infusion for low- or intermediate- risk PCa patients**. The incidence and severity of immune-mediated toxicities following a limited course of 3 infusions four weeks apart is not publically available. However, immune-mediated adverse events may occur at any time from the onset of therapy or after completion of treatment and may not be dose-dependent. Most immune-related adverse reactions, however, are low in severity and resolve with appropriate management, though fatal cases have been reported.

The frequency and median time to onset for the major immune mediated toxicities from pooled phase III datasets are shown in Table 1. These data relate to continuous therapy regimes with repeat nivolumab infusions at 2 week intervals. The incidence of toxicities grade 3 or above is <2% for all organ systems. Importantly, more than 50% of immune-mediated toxicities develop after several weeks of continuous treatment, therefore the frequency and risk of treatment-related adverse events following a restricted course of 3 infusions in this study is anticipated to be considerably lower than during licenced clinical use.

Table 1. Immune mediated adverse events after continuous monotherapy with Nivolumab

Immune-mediated toxicity	Frequency (%) *		Median (range) time to onset (months)	Corresponding number of doses at median time of onset **
	Any severity	Grade 3 or above		
Rash	25.6	0.9	1.4 months(0.0-113.7)	3
Diarrhoea / Colitis	12.6	1.3	1.4 months (0.0-20.9)	3
Pneumonitis	3.0	0.8	3.3 months (0.0-19.6)	7
Liver dysfunction/ Hepatitis	6.4	1.8	1.9 months (0.0-10.4)	4
Renal dysfunction	2.7	0.5	2.3 months (0.0-18.2)	5
Endocrinopathy				
Thyroid disorders	8.5	<0.1	2.8 months (0.0-14.0)	6

Adrenal insufficiency	0.4	0.2		
Pituitary disorders	0.4	0.2		

* From pooled dataset n = 2227 (CA209066, CA209037, CA209067 trials) nivolumab 3mg/kg across tumour types

** Based on standard licenced dosing interval of 2 weeks

Participants will be under continuous monitoring for checkpoint inhibitor toxicity. Established consensus treatment algorithms for investigation and management are in place and will be adopted according to site-specific clinical practice. All participants will be counselled on recognition and early reporting of potential treatment toxicities. The major immune-mediated toxicities associated with continuous use of nivolumab are:

Dermatological

Rash is the most common immune-related toxicity associated with anti-PD-1 therapy. The most frequent manifestation is with maculopapular rash, however, other presentations including urticarial dermatitis, vitiligo, lichenoid or psoriatic lesions are also possible. The majority of cases are grade 1 in severity. Isolated cases of Stevens-Johnson Syndrome and toxic epidermal necrolysis have been observed.

Diarrhoea

This presentation incorporates a spectrum of pathology ranging from increased stool frequency to active inflammation of the bowel (colitis) manifesting as abdominal pain, profuse diarrhoea, rectal bleeding and radiographic changes. The majority of cases are grade 1 or 2 in severity. Evaluation of diarrhoea and/or abdominal pain must include assessment for alternative aetiologies, in particular infective enteritis, constipation or obstruction and overflow.

Respiratory

Pneumonitis, or diffuse lung inflammation may present with shortness of breath, cough or chest pain. The major differential diagnoses include bacterial pneumonia and pulmonary embolism. The majority of cases are grade 1 or 2 in severity.

Hepatic and hepatobiliary

Immune-mediated liver toxicity may manifest with asymptomatic abnormalities in liver transaminases or total bilirubin during monitoring blood tests. Clinically apparent pancreatitis has been reported in $\leq 1\%$ of patients across clinical trials of continuous monotherapy in multiple tumour types. Laboratory abnormalities or subclinical disorders with elevation in serum amylase and lipase occur more frequently and may not warrant active intervention. Any suspected presentation requires detailed work up to exclude alternative aetiologies such as metabolic or obstructive liver / hepatobiliary pathologies.

Endocrine

Immune-mediated endocrinopathy may include thyroiditis with or without deranged thyroid function, adrenal insufficiency, diabetes mellitus or pituitary dysfunction. Presentation may involve non-specific symptoms including fatigue, anorexia, dehydration or headache and requires clinicians to retain a high index of suspicion. Endocrinopathy may require short or long term hormone replacement.

Renal dysfunction

Treatment-associated renal dysfunction manifesting as rise in serum creatinine with or without active urinary sediment may represent immune mediated or interstitial nephritis. However, careful attention and investigation are required to exclude alternative causes of renal impairment, including alternative nephrotoxic agents, pre-renal mechanisms and obstructive uropathy, particularly among participants with significant pelvic or retroperitoneal disease.

Other immune-mediated toxicities

Immune-mediated toxicity may rarely affect other organ systems. Immune-mediated neurological toxicity, including peripheral neuropathy, uveitis and ocular disorders, demyelination and myasthenic syndrome have, together been reported in <1% in cancer patients treated with continuous checkpoint inhibitor monotherapy in phase III clinical trials. Haematological disturbances including neutropaenia and thrombocytopenia may occur.

